A nationwide, parallel-group randomized controlled superiority trial is conducted comparing an adapted MBSR + SAU (intervention) with SOM + SAU (control). The intervention is an interactive adapted videoconferencing MBSR group-training. The training consists of eight 1,5 hour sessions twice a week during 4 weeks. The sessions will be held via interactive videoconferencing. Participants in the control condition will have the possibility to use a self-help daily mindfulness exercise (30 minutes) on a YouTube channel. In total the participants will receive 24 mindfulness and compassion exercises in 4 weeks. Treatment allocation is a 1:1 ratio. Assessments will be conducted at baseline (T0), mid-treatment (T1), and at 1 (T2), 4 (T3) and 7 (T4) months follow-up. Participants randomized to the SOM + SAU condition will be able to participate in an adapted MBSR intervention after they completed the study (7 months).

Randomization

Random assignment to adapted MBSR + SAU or SOM + SAU is electronically conducted by CastorEDC. Randomization is stratified by setting (3 levels: hospital, nursing home, other), prior mindfulness training (yes/no), and profession (3 levels: physician, nurse, other). Block randomization with predefined blocks are used (2 or 4) in order to ensure balanced groups. Diagnostic research assessors conducting clinical interviews were blinded to the treatment allocation.

Sample size

Based on Lai et al.[1], high post-exposure levels of depression, anxiety, insomnia and distress are expected (in 50-70% of healthcare workers). So far, no data exist on changes of these levels of distress in healthcare workers in the COVID-19 pandemic due to interventions.

Therefore, we aim to detect an effect-size of 0.4 ($\alpha=0.05$; $\beta=0.20$; two-tailed). When using t-tests, a sample size of 200 (100 in each arm) is needed. This will suffice to reveal a clinically relevant difference of 5 points on the PHQ-SADS[8] (scale of sum-score 0-78). To overcome attrition, we will increase the size of our groups with 10%. Thus, a total of 220 participants (110 in each group) will be included in this randomized controlled study.

Framework

Both primary and secondary outcomes will be assessed for superiority of an adapted MBSR + SAU above SOM + SAU.

Statistical interim analyses and stopping guidance

Not applicable

Timing of final analysis

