The Trimbos/iMTA questionnaire for Costs associated with Psychiatric illness (TiC-P) [25] will be used to collect information on direct healthcare use and paid and informal work-related productivity losses at 7 months. The EuroQol-5D-3L (EQ-5D) will be used to measure health-related quality of life.

COVID-19 related questions and mindfulness practice questions will be asked.

Analysis methods

Treatment effects at T4

Primary analyses will be performed on the intention-to-treat (ITT) sample. ANCOVA will be used to examine the main effect (PHQ-SADS) of the intervention at T4. Roughly, every month during approximately one year a group will start with the intervention (cohort). Due to the expected differences in these groups, cohort effects will be added. Therefore, a Linear Mixed Effect Model will be used for the analyses. Group (adapted MBSR + SAU / SOM + SAU) will be added as fixed effects, while controlling for baseline levels. A random effect for cohort will be added, and if applicable as a fixed effect. Cohen's *d* effect size will be calculated by dividing the adjusted group difference at T4 by the pooled standard deviation at T0. [26]

Difference in occurrence of psychopathology (present/absent) between adapted MBSR + SAU and SOM + SAU assessed by SCID-5 interview at T4 will be tested with Chi-square test.

Course to treatment effect at T4

The course of treatment effects from baseline to T4 for both primary and secondary outcomes (post-traumatic stress symptoms, insomnia, alcohol use, post-traumatic growth, positive mental health) at

T2, T3, and T4 will be evaluated with Linear Mixed Effects Models. Time, group (adapted MBSR + SAU / SOM + SAU) and their interaction will be added as fixed effects, while controlling for baseline levels. A random effect for participant and cohort (random slope and intercept) will be added. Heterogeneous first-order autoregressive (ARH(1)) covariance structure will be used, which assumes that measurements closer in time are more strongly related to each other. Restricted maximum likelihood will be used as estimation method to handle missing data. Cohen's *d* effects size will be calculated by dividing the adjusted group difference between the pooled means (T2, T3, T4) by the pooled standard deviations at T0.[26]

Moderation of the effect

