Moderation will be examined by adding the potential moderator and its interaction with group to the model. Separate models will be run for each possible moderator. The following possible moderators will be used: gender, age, work setting, profession, prior mindfulness training, adherence, baseline depressive, anxiety and somatic symptoms, and baseline perseverative thinking, mindfulness and self-compassion.

Mediation of the effect

Mediation analysis will be performed on per-protocol sample, using the multiple mediation model by Preacher & Hayes.[27] We will examine whether T0 to T1 change in potential mediators (mindfulness skills, self-compassion, and perseverative negative thinking) mediated T0 to T2 change in depressive, anxiety and somatic symptoms, post-traumatic stress symptoms, insomnia, post-traumatic growth and positive mental health.

Any adjustment for covariates

See above

Methods used for assumptions to be checked for statistical methods

Assumptions of normality will be checked and, in case of lack of normality, bootstrapping will be used to account for this problem.

Any planned sensitivity analyses for each outcome

Sensitivity analyses will be conducted by performing the primary and secondary analyses in the per-protocol (PP) sample. The per-protocol analysis set consists of subjects who have a minimum exposure of 4 MBSR sessions (intervention group (adapted MBSR + SAU)). Further sensitivity analysis will be performed depending on possible patterns in missing values and when relevant disbalance in covariates will be observed.

Any planned subgroup analyses for each outcome

Moderation will be examined by adding the potential moderator and its interaction with group to the model. Separate models will be run for each possible moderator. The following possible moderators

will be used: gender, age, profession, work setting, prior mindfulness training, baseline levels of depressive, anxiety and somatic symptoms.

Missing data

No imputation will be needed for baseline measures, because participants were only randomized if T0 was completed. The questionnaires will be filled in an online platform (CastorEDC), in which it is required to fill in an item before continuing to the next item. Therefore, we expect a low number of missing data.

Additional analysis

None

Harms

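### The three factors that stratify the randomisation are left out of the primary and longitudinal models, which makes the test conservative and costs some power if they are prognostic

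*SAP*

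**What the plan says.** Section 3 (Randomization) sets the design: "Randomization is stratified by setting (3 levels: hospital, nursing home, other), prior mindfulness training (yes/no), and profession (3 levels: physician, nurse, other". It continues: "Block randomization with predefined blocks are used (2 or 4) in order to ensure balanced groups". Under Trial design, "Treatment allocation is a 1:1 ratio".

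Section 6 (Treatment effects at T4) specifies the primary model as a linear mixed model: "Group (adapted MBSR + SAU / SOM + SAU) will be added as fixed effects, while controlling for baseline levels". A cohort effect (the monthly start group) is added as random or, if applicable, fixed.

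Section 6 (Course to treatment effect at T4) specifies the longitudinal models: "Time, group (adapted MBSR + SAU / SOM + SAU) and their interaction will be added as fixed effects, while controlling for baseline levels", with random effects for participant and cohort.

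Under the heading "Any adjustment for covariates" the SAP only refers the reader back to the text above it, and nothing above adds the stratification factors. They appear in Section 6 only as candidate moderators, one at a time: "Separate models will be run for each possible moderator". A further sensitivity analysis is foreseen if a relevant covariate imbalance is seen, but it names no covariates.

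**The concern.** Stratified blocking forces the arms to be nearly equal on setting, prior training and profession. If these factors are related to month-7 distress after baseline is accounted for, the true sampling variance of the group difference falls. A model that omits them does not register this: it counts their contribution as residual noise and reports a standard error that is too large. The confidence interval is then wider than it needs to be, the test rejects less often than 5% under the null, and power is given up that the design had already secured.

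The other parts of the SAP do not fill the gap:

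- **Moderator models.** They address question II.4, hold one factor each, and do not supply the primary estimate.
- **Cohort.** It is the start group and not a stratification factor.
- **Imbalance-triggered sensitivity analysis.** It would seldom fire for factors that the randomisation balances, and it leaves the primary result unchanged.

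**Working it through.** **Inputs from the SAP (Section 3, Sample size; Section 4).** d = 0.4, two-sided alpha 0.05, power 80%, t-test. "When using t-tests, a sample size of 200 (100 in each arm) is needed". A 10% increase gives 220. Strata: 3 × 2 × 3 = 18, in blocks of 2 or 4.

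**Assumed, not in the SAP.** R² is the share of outcome variance left after baseline that the three factors explain; range 0 to 0.15. r is the correlation of baseline with month-7 PHQ-SADS; 0.4 or 0.6.

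**Step 1: the SAP's own figure.** The normal approximation gives 99 per arm (198). The noncentral t gives 80.4% power at 100 per arm. The stated 200 is reproduced, and 200 × 1.10 = 220.

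**Step 2: standard error and type I error.** Let k = √(1 − R²). With strata balanced, the true SE is k times the SE that the unadjusted model reports.

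- SE ratio (reported to true) = 1/k
- Type I error = 2 × [1 − Φ(1.96/k)]

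| R² | SE ratio | Type I error, unadjusted |
|---|---|---|
| 0 | 1.000 | 5.0% |
| 0.05 | 1.026 | 4.4% |
| 0.10 | 1.054 | 3.9% |
| 0.15 | 1.085 | 3.4% |

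**Step 3: power with 100 per arm.** Unadjusted power = Φ((ncp − 1.96)/k). Adjusted power = Φ(ncp/k − 1.96).

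- (a) d = 0.4 in residual-SD units: ncp = 0.4 × √50 = 2.83
- (b) d = 0.4 on the raw SD: ncp = 2.83/√(1 − r²), which is 3.09 at r = 0.4 and 3.54 at r = 0.6

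| R² | (a) unadj. / adj. | (b) r = 0.4 | (b) r = 0.6 |
|---|---|---|---|
| 0 | 80.7 / 80.7 | 87.0 / 87.0 | 94.2 / 94.2 |
| 0.05 | 81.4 / 82.7 | 87.6 / 88.6 | 94.7 / 95.2 |
| 0.10 | 82.0 / 84.6 | 88.2 / 90.2 | 95.2 / 96.1 |
| 0.15 | 82.7 / 86.6 | 88.9 / 91.7 | 95.6 / 97.0 |

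From unrounded values, the losses in points at R² = 0.05, 0.10 and 0.15 are 1.3, 2.6 and 3.9 in (a); 1.0, 2.0 and 2.8 at r = 0.4; 0.5, 1.0 and 1.3 at r = 0.6.

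**Step 4: cost in participants.** Setting Φ((ncp × √(N/200) − 1.96)/k) equal to the adjusted power and solving for N at R² = 0.15 gives 22, 20 and 18 extra participants in the three cases. The SAP's whole attrition allowance is 20.

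**Step 5: simulation with real blocking.** Two simulations of 6,000 trials per scenario used the 18 strata and blocks of 2 or 4, with assumed stratum shares and no cohort effect.

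- N = 200, outcome taken as the residual after baseline, R² = 0.10: type I error 3.9% unadjusted and 5.0% adjusted; power 81.3% and 84.0%.
- 220 randomised, 20 dropped at random, r = 0.5, R² = 0.15: type I error 3.7% and 5.1%; power 91.5% and 93.9%; SE ratio 1.083.

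Monte Carlo error is about 0.3 points on type I error and 0.5 on power. The formulas and the simulations agree.

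**Step 6: cost if the factors are not prognostic (R² = 0).** The 5 extra degrees of freedom cost about 0.01 point of power by formula and 0.15 to 0.3 point in the simulations.

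**The case against.** The strongest reply is that nothing in the planned analysis is invalid. The estimate is unbiased, the test errs on the safe side, and unadjusted power is at or above the planned 80% in every case computed by formula. Baseline PHQ-SADS, the same scale as the outcome, is already in the model and may absorb most of what the three factors could explain. The SAP gives no R², and at 0.05 to 0.10 the loss on the raw-SD scale is only 0.5 to 2.0 points. That scale is the closer match, because the SAP sizes a t-test and divides the adjusted difference by the pooled SD at T0. The largest figure, 3.9 points, depends on the residual-SD reading.

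All of this stands as a limit on size. Two further limits also stand. The type I error statement concerns this omission alone: the calculations include no cohort effect and assume random dropout, so they do not certify the whole planned model. The longitudinal models share the omission, but its effect there was not quantified.

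It can also be said that the reference back to earlier text is a definite specification (baseline and cohort), and that each factor does get a main effect in a moderator model. True, but neither puts the three factors into the models that answer the primary and longitudinal questions. None of these replies offers a reason to leave the factors out.

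**Conclusion.** The concern holds. The primary T4 model and the longitudinal models omit all three stratification factors, and no other provision of the SAP puts them in. The consequence is lost efficiency, conditional on the factors being prognostic beyond baseline. For an assumed R² of 0 to 0.15, type I error is 5.0% down to 3.4% and the power loss is 0 to 3.9 points, or 0 to 2.8 on the raw-SD scale with a baseline correlation of 0.4 or more. The sample size of 200 is not undermined and no bias is claimed. The change is worth making because the possible gain is real and the cost is close to nil.

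**What to change.** Replace the back-reference in the covariate-adjustment entry of Section 6 with: *The primary T4 model and the longitudinal linear mixed models include setting (hospital, nursing home, other), prior mindfulness training (yes/no) and profession (physician, nurse, other), as recorded for randomisation, as fixed main effects, whatever their p-values.*

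The cost is one sentence and 2 + 1 + 2 = 5 degrees of freedom out of about 200. Stratified allocation requires all three values, so they are known for everyone randomised. Main effects are enough; a term for each of the 18 strata would be sparse at this sample size. The imbalance-triggered sensitivity analysis can stay. The chi-square test for SCID-5 is outside this change, because adjusting it would mean replacing the method and not merely adding terms.

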All outcomes will be analyzed collectively after the T4 measurement and the SCID5 interviews have taken place in the last participants (anticipated being June 2022).

Timing of outcome assessments

At baseline participants complete the questionnaires used for our primary/secondary outcomes. The same questionnaire are send after 1 month (post-intervention), and after 4 and 7 months. To measure possible mediators three questionnaires are used at mid-treatment (2 weeks after start of

the intervention). At 7 months the occurrence of psychopathology is measured by the Structured Clinical Interview for DSM-5 (SCID5).

Section 4: Statistical Principles

Confidence intervals and P values

Level of statistical significance

All applicable statistical tests will be 2-sided and will be performed using a 5% significance level.

Description and rationale for any adjustment for multiplicity

Not applicable

Confidence intervals to be reported

All confidence intervals presented will be 95% and two-sided.

Adherence and protocol deviations

Definition of adherence to the intervention and how this is assessed

Adherence implies that participants attended ≥ 4 sessions in the adapted MBSR + SAU group. The MBSR trainer will keep an attendance register.

Participants in the SOM + SAU group will be asked at timepoint T1 and T2 how often they did a mindfulness exercise in the last two weeks.

Analysis populations

All analyses will be conducted in SPSS version 25 and will be performed as intention-to-treat (ITT). The intention-to-treat population will include all randomized patients, according to the treatment they were randomized to receive. Secondary, per protocol analyses will be conducted.

Section 5: Trial Population

Screening data

Potential participants fill out an online registration form expressing their interest for the study. Next, a screening interview by telephone is planned. Study information will be given and in- and exclusion criteria will be checked during this interview. All screened potential participants and their eligibility will be registered.

Eligibility

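### The primary model's cohort term leaves the coding of self-help controls open and has no MBSR-only group term, so the treatment standard error, or the effect itself, rests on an unstated choice

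*SAP*

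**What the plan says.** Section 3 (Trial design) describes the two arms differently. For MBSR: "The intervention is an interactive adapted videoconferencing MBSR group-training". For SOM: "Participants in the control condition will have the possibility to use a self-help daily mindfulness exercise (30 minutes) on a YouTube channel". The randomization strata in the same section are setting, prior mindfulness training and profession; cohort is not one of them.

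Section 6 (Treatment effects at T4) introduces cohort: "Roughly, every month during approximately one year a group will start with the intervention (cohort". It gives the reason for modelling it: "Due to the expected differences in these groups, cohort effects will be added". It then specifies the term: "A random effect for cohort will be added, and if applicable as a fixed effect". Treatment group is a fixed effect and the model adjusts for baseline.

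The model for the course of the effect over T2 to T4 repeats the term: "A random effect for participant and cohort (random slope and intercept) will be added". Neither model says how SOM participants are coded.

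**The concern.** Sharing a trainer and fellow participants can make outcomes within an MBSR group alike. SOM participants share no such group, so this source of correlation exists in one arm only. A single cohort term handles it correctly only under some codings, and the SAP's wording permits several:

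- **(a) Cohort is a start period shared by both arms, random or fixed.** The treatment effect is then a within-cohort contrast. A shared cohort effect cancels from it, but a difference between MBSR groups does not, and the model leaves that variance out of the standard error (SE).
- **(b) Cohort is the MBSR group, random.** This works if SOM participants carry no group effect or are each their own cluster. It is badly conservative if all SOM participants form one cluster.
- **(c) Cohort is the MBSR group, fixed.** The treatment indicator is the sum of the MBSR-group indicators, so the effect is not identified.

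The strata supply no cohort label for SOM participants, and no rule says when the fixed version applies. The choice therefore stays open until analysis, for the primary outcome.

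**Working it through.** **Inputs from the SAP.** Two-sided 5% level (Section 4). From Section 3 (Sample size): effect 0.4 SD, 80% power, 100 per arm, 110 per arm after a 10% increase. About 12 monthly cohorts (Section 6).

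**The SAP's own figure.** The noncentral t calculation for 0.4 SD gives 100 per arm (power 80.7%), and 200 × 1.10 = 220. The stated size reproduces. It treats observations as independent. Since 5 points are equated with 0.4 SD, the implied SD is 5 / 0.4 = 12.5 points.

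**Assumptions.** 12 cohorts with 9 per arm each (12 × 9 = 108 per arm, the balanced layout nearest 110); one MBSR group per cohort; SD 1 in each arm; clustering in MBSR only. The SAP gives no ICC, so 0 to 0.10 is shown.

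**Step 1: true SE at ICC 0.05.**
- MBSR mean: [1 + (9 − 1) × 0.05] / 108 = 1.40 / 108
- SOM mean: 1 / 108
- SE = √(2.40 / 108) = 0.149

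**Step 2: SE reported under coding (a), shared fixed cohort.** Residual df = 216 − 13 = 203. The expected residual sum of squares has three parts:
- within MBSR cells: 96 × 0.95 = 91.2
- within SOM cells: 96 × 1 = 96
- cohort-by-arm: 11 × 4.5 × (0.05 + 0.95/9 + 1/9) = 13.2

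The total is 200.4, and 200.4 / 203 = 0.987. SE = √(0.987 × 2 / 108) = 0.135. The between-group variance enters only through 11 of 203 df, so it is almost wholly diluted.

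**Step 3: type I error under (a).** The critical value 1.972 × 0.135 / 0.149 is about 1.79 true SEs, which gives roughly 7.4%; simulation gives 7.5%.

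**Step 4: simulated type I error (%) by coding.**

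| Coding | ICC 0 | 0.02 | 0.05 | 0.10 |
|---|---|---|---|---|
| (a) shared, fixed | 5.0 | 6.0 | 7.5 | 10.2 |
| (a) shared, random | 5.1 | 6.0 | 7.6 | 10.2 |
| (b) MBSR-only random, SOM no group effect | 4.1 | 4.5 | 4.8 | 5.1 |
| (b) SOM as singletons | 4.0 | 4.4 | 4.7 | 4.9 |
| (b) all SOM as one cluster | 2.8 | 2.5 | 1.9 | 1.2 |
| Shared cohort plus MBSR-only group (the fix) | 4.3 | 4.7 | 5.0 | 5.5 |

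Monte Carlo error is about 0.1 point or less. Random codings use Satterthwaite df, with variance components estimated at zero dropped from the df; keeping them gives 3.3–5.2% for the last row. With all SOM participants as one cluster, the model SE runs from 0.198 to 0.350 against a true 0.136 to 0.161.

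**Step 5: sensitivity.**
- Shared fixed at ICC 0.05 gives 8.0% with 10 cohorts of 11 per arm and 7.2% with 14 of 8.
- Adding a baseline covariate (assumed r = 0.5, ICC of the adjusted outcome) gives 4.9 / 6.0 / 7.8 / 9.9%, so baseline adjustment does not remove the problem.
- With a shared cohort variance of 0.05 added, the last row becomes 3.9 / 4.1 / 4.7 / 5.1%. MBSR-only random with no SOM group effect becomes conservative: 2.8 / 3.0 / 3.4 / 3.8%.

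**Step 6: coding (c).** Intercept, treatment and 12 MBSR-group indicators make 14 columns of rank 13. The rank is still 13 with the treatment column removed, so the data carry no separate information on treatment.

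**Step 7: separate check.** A second simulation (110 per arm, 1,500 trials, Wald z) gave type I error of 8.3% for shared coding and 5.4% for an MBSR-only term at ICC 0.05. With SOM as one cluster, power at 0.4 SD was 39%.

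**Step 8: effect on the verdict.** The smallest significant difference is the t quantile times the SE. At ICC 0.05 it is 1.972 × 0.135 = 0.267 SD under (a), and with about 31 df 2.04 × 0.149 = 0.304 SD in a model carrying the groups. In points: 0.267 × 12.5 = 3.3 against 0.304 × 12.5 = 3.8. At ICC 0.02 the pair is 0.268 and 0.287 SD; at 0.10 it is 0.265 and about 0.33 SD. An observed 0.4 SD at ICC 0.05 gives p = 0.0035 and p = 0.012.

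**The case against.** Four points deserve weight.

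- **Some codings are unlikely.** Non-identification needs cohort to be both fixed and MBSR-only, and software would flag it. One cluster for all SOM participants is a remote choice. This is fair. The realistic choice is between a shared cohort and an MBSR-only term.
- **A shared start period is a natural reading.** Both arms run for four weeks, and SOM participants are also questioned at T1 and T2, so they can be given a start date. This is true, but Section 3 labels the MBSR arm as the intervention, and Section 6 defines cohort by groups starting the intervention. Both readings stand, and the shared one gives too small an SE whenever MBSR groups differ.
- **The differences may be purely calendar effects.** If so, shared coding is correct (the second simulation gave an SE ratio of 1.00 and type I error of 5.3%). That stands. But calendar variance does not repair coding (a) when group variance is also present: in the shared-fixed model it cancels from the within-cohort contrast.
- **The ICC is unknown and the effect may be small.** At ICC 0.01 to 0.02, shared coding understates the SE by only about 2–4%, and clustering may have weakened by T4, six months after the groups end. This stands and limits the weight of the point. The undefined SOM label and the missing criterion for fixed cohorts do not depend on any ICC.

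**Conclusion.** The concern holds. The SAP's stated reason for the mixed model is that groups differ, yet its cohort term does not determine whether that variation reaches the SE of the primary contrast.

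Under the shared reading, the excess over 5% is about 1 point at ICC 0.02, 2.5 points at 0.05 and 5 points at 0.10. These sizes rest on an assumed ICC, about 12 groups, one group per cohort and a balanced layout without attrition. A result near the planned 0.4 SD would be significant either way at ICC 0.05. The point should be fixed before the data are analysed, but it does not threaten the design.

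**What to change.** In Section 6:

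1. Define cohort as the start period for participants of both arms, and training group for MBSR participants.
2. Name one primary model: fixed treatment and baseline PHQ-SADS; random cohort intercept; random training-group effect in the MBSR arm only (cohort-by-MBSR if each cohort has one group), with SOM participants carrying no group effect; Satterthwaite df.
3. Delete the clause that allows cohort as a fixed effect.
4. Analyse MBSR participants in the training group they were scheduled for, including those who never attended. This follows from Section 4: "The intention-to-treat population will include all randomized patients, according to the treatment they were randomized to receive".
5. Carry the same MBSR-only term into the T2–T4 model, and state there to whom the cohort intercept and slope apply.

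The cost is SAP wording and one random term; enrolment does not change. At ICC 0.05 the SE becomes about 0.148–0.151 instead of 0.135. If the ICC is zero, the test is slightly conservative (3.9–4.3%).

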Participants are eligible if they are healthcare workers who either currently or recently have been working in the acute care for COVID-19 patients on COVID-19 wards/intensive care units or in primary care or nursing homes. The exclusion criteria are insufficient comprehension of the Dutch language, and inability to access the interactive videoconferencing. The number of ineligible participants will be reported with reasons for ineligibility. Eligible participants who refrain from participating before randomization will be reported with reasons for withdrawal.

Recruitment

A CONSORT flow diagram will be used to summarize the number of participants who were:

- Assessed for eligibility at screening
 - Eligible at screening
 - Ineligible at screening*
- Eligible and randomized
- Eligible but not randomized*
- Received the randomized allocation
- Did not receive the randomized allocation*
- Discontinued the intervention*
- Lost to follow-up*
- Randomized and included in the primary analysis
- Randomized and excluded from the primary analysis*

*reasons will be provided.

Withdrawal/follow-up

The level of consent of withdrawal will be classified as “consent to continue data collection” or “no further data collection”. The numbers (with reasons) of losses to follow-up (drop-outs and withdrawals) over the course of the trial will be summarized by intervention arm and presented in the CONSORT diagram.

Baseline patient characteristics

Participants will be described by intervention arm with respect to age, gender, marital status, having children, level of education, previous and current psychological treatment, prior mindfulness training, work setting, profession, working years in healthcare.

Categorical data will be summarized by numbers and percentages. Continuous data will be summarized by mean, SD and range if data are normal distributed and median, IQR and range if data are skewed.

Section 6: Analysis

Outcome definitions

Primary outcome

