The primary outcome will be the change in psychological distress between baseline and 7 months follow-up, as assessed by the total score on the *Patient Health Questionnaire – Somatic, Anxiety and Depressive Symptoms (PHQ-SADS)*[8] scale. This is a 31-item self-report measurement combining PHQ-9, GAD-7, and PHQ-15. The 9-item *Patient Health Questionnaire (PHQ-9)*[9] evaluates the presence of the nine DSM-5 criteria of a depressive episode in the past 2 weeks: depressed mood, anhedonia, trouble sleeping, feeling tired, change in appetite or weight, guilt or worthlessness, trouble concentrating, feeling slowed down or restless and suicidal thoughts. There are four answer categories: 0 (not at all), 1 (few days), 2 (more than half the days) and 3 (almost every day). The 7-item *Generalized Anxiety Disorder (GAD-7)*[10, 11] scale measures severity of anxiety. Frequency of anxiety symptoms are rated within the last 2 weeks on a 4-point scale ranging from 'not at all' to 'almost every day'. The 15-item *Patient Health Questionnaire (PHQ-15)*[12] is a self-administered questionnaire includes 15 symptoms that account for more than 90% of all symptoms seen in primary care. Subjects were asked for the last 4 weeks to rate the severity of 15 symptoms as 0 (not bothered at all), 1 (bothered a little), and 2 (bothered a lot).

Cut-off scores of ≥ 5 , ≥ 10 , and ≥ 15 representing mild, moderate, and severe symptoms, respectively, on all three scales. The total score of the PHQ-SADS will be calculated by the sum of PHQ-9, GAD-7 and PHQ-15, and ranges from 0 to 78.

Confirmatory factor analysis will be performed, in line with the research on the PHQ-ADS[13], to investigate sufficient unidimensionality of the PHQ-SADS to support the use of the total score as a composite measure for depression, anxiety and somatic symptoms.

Secondary outcome

The *Structured Clinical Interview for DSM-5 Axis I Disorders Research Version (SCID5)* will be used to retrospectively assess the occurrence of psychopathology (depression, anxiety disorder, posttraumatic stress disorder (PTSD), insomnia, substance abuse, somatoform disorder, obsessive compulsive disorder, eating disorder, illness anxiety disorder, adjustment disorder) at 7 months follow-up. The psychometric properties of the Dutch translation of the SCID have been shown to be excellent.[14] The SCID-5 will provide dichotomous score (presence or absent of psychopathology).

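### The SCID-5 chi-square test is a complete-case analysis under an all-randomised ITT declaration, and no named method covers a missed interview

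*SAP*

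**What the plan says.** The SCID-5 is a secondary outcome with its own research question (II.1). It is scored present or absent and is obtained once, by interview at 7 months (Section 3, Timing of outcome assessments; Section 6, Secondary outcome). The analysis is a single sentence in Section 6, Treatment effects at T4: "Difference in occurrence of psychopathology (present/absent) between adapted MBSR + SAU and SOM + SAU assessed by SCID-5 interview at T4 will be tested with Chi-square test".

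Section 4, Analysis populations, puts all analyses on an intention-to-treat footing and defines the population: "The intention-to-treat population will include all randomized patients, according to the treatment they were randomized to receive".

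Four other places touch on missing data:

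- Section 6, Course to treatment effect at T4, relies on restricted maximum likelihood, within the linear mixed models for the repeated scales.
- Section 6, Missing data, says that T0 is complete for everyone randomised and expects few gaps afterwards for this reason: "The questionnaires will be filled in an online platform (CastorEDC), in which it is required to fill in an item before continuing to the next".
- Section 6, Any planned sensitivity analyses, promises further work that will depend on what the missing values look like. It names neither a method nor an outcome.
- Section 5, Withdrawal/follow-up, foresees two kinds of withdrawal: "The level of consent of withdrawal will be classified as “consent to continue data collection” or “no further data collection". Losses are to be reported by arm, with reasons.

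Section 3, Sample size, enlarges the groups by 10% for attrition, to 110 per arm.

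**The concern.** A chi-square test on a two-by-two table has no cell for a participant without a diagnosis. Followed as written, the plan drops everyone who was not interviewed from an endpoint that it declares to be analysed in all randomised participants. Restricted maximum likelihood belongs to the models for continuous scales. Forced item entry stops skipped questions in an online form; it cannot stop a missed interview.

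This matters if the interviewed are a selected group and the selection differs by arm. The SAP gives reasons why it might. One arm attends eight live group sessions and the other has an optional video channel. Only the control arm is offered the MBSR course once its 7 months are complete, which is a reason to stay that the other arm lacks. Meanwhile the plan leaves unused the questionnaire scores on depression, anxiety, somatic symptoms, post-traumatic stress and insomnia that some non-interviewed participants will have.

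**Working it through.** **1. The plan's own figures.** An effect size of 0.4 with two-sided alpha 0.05 and 80% power needs 99.08 per arm by the t-test, so 100 per arm; the stated 200 reproduces. Enlarged by 10%: 100 × 1.10 = 110 per arm, 220 in total. If 10% are then lost, 110 × 0.90 = 99 per arm remain, and 22 of 220 have no interview. (Counting only the added participants as the allowance gives 20.) The SAP states no SCID-5 prevalence and no interview completion rate, so every rate below is an assumption.

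**2. Spurious difference when the arms are truly equal.** Let p be the true prevalence, and let mc and mn be the proportions without an interview among cases and non-cases. The prevalence among those interviewed is

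p(1 − mc) / [p(1 − mc) + (1 − p)(1 − mn)].

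Take p = 0.30 in both arms. Differences are MBSR minus SOM.

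- SOM, mc = mn = 0.10: 0.27 / (0.27 + 0.63) = 30.0%.
- MBSR, mn = 0.10, mc = 0.20: 0.24 / (0.24 + 0.63) = 27.6%, a difference of −2.4 points (13% missing in the arm).
- MBSR, mn = 0.10, mc = 0.30: 0.21 / (0.21 + 0.63) = 25.0%, a difference of −5.0 points (16% missing in the arm).

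The next rows fix total loss per arm and let cases be lost three times as often as non-cases. The type I error of the chi-square test comes from 40,000 simulated trials with 110 per arm.

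| Missing, MBSR / SOM | Loss tied to diagnosis in | Spurious difference | Type I error |
|---|---|---|---|
| 10% / 10% | neither arm | 0 | 0.049 |
| 10% / 10% | both arms | 0 | 0.050 |
| 10% / 10% | MBSR only | −2.9 points | 0.075 |
| 15% / 5% | both arms | −3.3 points | 0.078 |
| 20% / 10% | MBSR only | −6.6 points | 0.173 |

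For scale, the standard error of the difference with 99 per arm is √(0.30 × 0.70 × 2/99) = 6.5 points. If the symptom-related loss were in the SOM arm instead, the sign would reverse.

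**3. How far an invented result could move.** Suppose 20/99 against 35/99, with 11 missing per arm: −15.2 points, p = 0.017. Counting all missing as cases gives 31/110 against 46/110: −13.6 points, p = 0.034. The extreme bounds are 20/110 − 46/110 = −23.6 and 31/110 − 35/110 = −3.6 points (p = 0.56 at the latter). With 22 and 6 missing, 18/88 against 36/104 gives −14.2 points, p = 0.030. Counting all missing as cases then gives 40/110 against 42/110: −1.8 points, p = 0.78.

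**4. What imputation from questionnaires can repair.** In simulations with 110 per arm, missing diagnoses were filled by prediction from T0 and T2 scores. When loss depended on the T2 score in MBSR only, a complete-case bias of about −2.4 to −2.8 points fell to about 0. When loss depended on the diagnosis itself, as in step 2, the bias went only from −2.3 to −1.8 and from −5.2 to −4.2 points. That leaves 1.8/2.3 = 78% and 4.2/5.2 = 81%. T4 scores were not tested and might help where they exist.

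**The case against.** The strongest reply is that the SAP does not ignore missing data for this outcome. Its sensitivity clause sits under a heading that applies to each outcome, and the SCID-5 is one of them. That stands as partial mitigation, but the clause is triggered by the data, names no method, and leaves the complete-case test as the reported result.

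A reader might infer that everyone who withdraws is lost to the SCID-5. The SAP does not support that. Section 5 keeps a class of withdrawals who agree to further data collection, and nothing limits interviews to those who finished the course. Reporting losses by arm with reasons would also make an imbalance visible.

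A reader might also infer that the II.1 comparison is biased as it stands. That is not shown. The prevalence, the loss rates and the one-arm symptom-related loss are all assumed. Most scenarios here lose more than 10% in the MBSR arm, and the 2 to 5 point errors are under one standard error.

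A third temptation is to say that imputing from questionnaires removes the problem. Step 4 shows that it does so only when the scores explain the loss. Nor would a large model be safe: six scales at four visits plus five stratification indicators make 29 predictors, against about 0.30 × 99 ≈ 30 cases per arm if fitted by arm. Only T0 is guaranteed for those without an interview.

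**Conclusion.** The inconsistency holds on the text: an endpoint declared ITT in all randomised participants has a test that can use only the interviewed, and no named method fills the gap. At the SAP's own attrition allowance about 22 of 220 participants are affected.

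Bias is conditional. It needs loss that is related to symptoms and that differs by arm in rate or mechanism. Under an assumed 30% prevalence and one-arm symptom-related loss, it is about 2 to 5 points, and 6.6 points at 20% against 10% missing. It is near zero if loss has the same rate and the same relation to symptoms in both arms. The primary outcome is not touched. The point is worth correcting because II.1 is a research question in its own right and the remedy uses data already being collected.

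**What to change.** Replace the SCID-5 sentence in Section 6 with a rule fixed before the outcome data are examined by arm:

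1. **Main analysis.** All randomised participants, with missing present/absent status multiply imputed. Use one small model: arm, baseline and latest available PHQ-SADS, PCL-5 and ISI totals, and the stratification factors. That is 1 + 6 + 5 = 12 predictors fitted to both arms together. Pool an estimate that has a standard error, such as the risk difference or log odds ratio, with its 95% confidence interval.
2. **Complete-case check.** Keep the chi-square test in interviewed participants and label it as such.
3. **Sensitivity to loss that depends on diagnosis.** Pre-specify a delta-adjusted or bounding analysis over a stated range, varied separately by arm. As a guide to the range, the scenarios in step 2 with mc = 0.20 and 0.30 against mn = 0.10 imply odds of a diagnosis among the missing of 0.25/0.111 = 2.25 and 0.429/0.111 = 3.9 times those among the interviewed. The 20% case (mc = 0.375, mn = 0.125) implies 0.6/0.143 = 4.2. A multiplier running from 1 to 5 would span these.
4. **Reporting.** Give the number interviewed by arm, with reasons for each missing interview.

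The cost is SAP wording, an imputation model resting on a missing-at-random assumption, and a modest extra analysis step. No new visits or data are needed.
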